7.2 Dose modification

Dose modification is handled autonomously by the iLet™ based on the CGM sensor readings and the user interaction with the iLet™ e.g. meal announcements. Therefore, there is no standard insulin titration algorithm in this trial.

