Appendix 16.1.1

~~CONFIDENTIAL~~

Date:
Version:
Status:

25 October 2019
1.0
Final

Novo Nordisk

Global and country key Novo Nordisk staff

Attachments I and II (if applicable) to the protocol are located in the Trial Master File.

Content: Global key staff and Country key staff

Protocol Amendment

no 1

**to Protocol, version 2
dated 07 June 2018**

Trial ID:NN1218-4360

**An Exploratory Trial investigating the Safety and Efficacy of Fast-acting Insulin Aspart in a
Closed-loop Insulin Delivery System (bionic pancreas) in Adults with Type 1 Diabetes**

**Trial phase: 2
Applicable to all countries**

~~This confidential document is the property of Novo Nordisk. No unpublished information contained herein may be disclosed without prior written approval from Novo Nordisk. Access to this document must be restricted to relevant parties.~~

Table of Contents

1	Introduction including rationale for the protocol amendment.....	3
2	Changes to protocol	3
3	Changes to subject informed consent	11

1 Introduction including rationale for the protocol amendment

This protocol amendment will serve to address the comments raised by the health authorities, specifically the US Food and Drug Administration (FDA) comments received during the Investigational Device Exemption (IDE) review.

The changes are mainly related to safety of the subject.

In this protocol amendment:

- Any new text is written *in italics*.
- Any text deleted from the protocol is written using ~~strike through~~.

Protocol has been amended to include the following major changes:

- Addition of exclusion criteria related to the use of acetaminophen
- Extension of “in-patient” period to 2 days
- Addition of individual subject’s discontinuation criteria
- Addition of trial stopping criteria
- Addition of further instructions for subjects in case of a hyperglycaemia or hypoglycaemia

A number of inconsistencies has been found and corrected and minor clarifications have been added. The subject informed consent has been updated accordingly to the changes implemented.

2 Changes to protocol

Section 1.2.2: Key exclusion criteria

- *Unwilling or unable to avoid acetaminophen throughout the trial*

Section 2: Flowchart

Footnote

h) Subject will spend ~~the 1st-2~~ nights at a hotel for close observation during each treatment period and each cross-over visit

Section 5.1: Overall Design

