Novo Nordisk will provide the aforementioned non-investigational medical devices (except StudyPhone with CGM app and *Remote Monitoring app*) to the subjects along with the paper diary.

For complaints related to the BG meter, *ketone meter*, infusion set or CGM device, the investigator must contact the device manufacturer's technical support according to Operator's Manuals provided with the BG meter, *ketone meter*, infusion set and the CGM device.

Training in the medical devices

iLet™

- How to replace the PumpCart®
- How and when to replace the batteries
- Troubleshooting in case of iLet™ failure or any technical problems
- *How to react in case of an alarm*

CGM – Dexcom G5®

- How and when to change the sensor
- How and when to calibrate the sensor
- How to use the CGM app on StudyPhone
- *How to react in case of an alarm*

BG Measurement - Contour® Next One

- When to perform self-measured plasma glucose (SMPG) measurements
- How and where to report the SMPG measurements
- ~~How and when to perform ketone measurement~~

Ketone measurement - Precision Xtra®

- *How and when to perform ketone measurement*

Section 7.8: Treatment after the end of the trial

When discontinuing trial product, the subject should be transferred *back to the insulin a suitable marketed product that was used for CSII therapy prior to the initiation of the trial at the discretion of the investigator.*

Section 8.1: Discontinuation of trial treatment

The subject must be discontinued from trial treatment, if the following applies:

5. *≥2 episodes of severe hypoglycaemia (see Appendix 7 for definition), possibly/probably related to investigational medicinal product and/or investigational medical device*

6. *Diabetic ketoacidosis possibly/probably related to investigational medicinal product and/or investigational medical device*

8.1.4: Trial stopping criteria

If any of below listed criterion are met, then the PI must suspend the further treatment of all subjects via the iLet™ and communicate the same to Novo Nordisk within 24 hours. Novo Nordisk safety committee will then evaluate the need for further investigation and makes the final decision on stopping the trial. All subjects must be transitioned to their usual CSII treatment until the final decision on stopping the trial has been made.

- *≥3 subjects experience any serious adverse events possibly/probably related to investigational medical device*

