- *≥3 subjects experience any severe hypoglycaemic episodes (see Appendix 7 for definition) possibly/probably related to investigational medical device*
- *≥3 subjects experience any diabetic ketoacidosis possibly/probably related to investigational medical device*

Section 9.2.1: Time period and frequency for collecting AE and SAE information

Table 9-1 AEs requiring additional data collection (via specific event form)

Event type	AE requiring additional event form
Hypoglycaemic episode ^a	X
Infusion site reaction ^b	X
Medication error ^c	X

^a Non-serious hypoglycaemic episode should only be reported on the hypoglycaemic episode form. *All severe hypoglycaemic episodes are qualified as SAEs and should be reported on the AE form, SIF and Hypoglycaemic episode form. Refer to Section 9.2.6 and Appendix 4 for reporting details*

Section 9.2.6: Disease-related events and/or disease-related outcomes not qualifying as an AE or SAE

Hypoglycaemia

Hypoglycaemic episodes should follow the below reporting:

- Non-serious hypoglycaemia must be reported on a hypoglycaemic episode form.
- *All severe hypoglycaemic episodes are qualified as SAEs and should be reported on a hypoglycaemic episode form, an AE form and a safety information form. One AE form and*

safety information for m can cover several hypoglycaemic episode forms, if the subject has not recovered between the episodes. *Severe hypoglycaemic episodes should follow the same reporting timelines as SAEs.*

~~If the hypoglycaemic episode fulfils the criteria for an SAE then in addition to the above, an AE form and a safety information form must also be filled in.~~

Section 9.5.1: Change of infusion set

Infusion sets must be replaced if any change in the insulin solution or occlusion is perceived by the subject, e.g. because of an iLet™ alarm indicating an occlusion or other observations pointing towards obstruction of the insulin flow. *Infusion sets should also be changed in case of prolonged hyperglycaemia and if the ketone measurement is positive.* Infusion set changes can be considered as a ‘non-routine change’ or ‘routine change’.

Section 9.10: Continuous glucose measurement

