Subjects should be instructed to avoid medications with acetaminophen/paracetamol while wearing the CGM sensor. These medications may affect the performance and readings of the CGM sensor (e.g. false high CGM readings)⁷⁻⁹. *If a subject inadvertently takes acetaminophen during the trial, they will be instructed to contact study staff. Site staff will closely monitor their CGM readings and instruct the subject to measure BG using the BG meter to verify CGM readings as frequently as needed. If the BG is closely correlated with the subject’s CGM glucose, study staff will continue to monitor closely. If CGM glucose is consistently higher than BG by >20 mg/dL(1.1 mmol/L) for BG ≤100 mg/dL (5.55 mmol/L) or >20% for BG >100 mg/dL(5.55 mmol/L), then the study staff may temporarily discontinue the iLet™ for the duration of action of the acetaminophen.*

Also, subject should be instructed to remove the Dexcom G5 sensor, transmitter, and receiver before x-ray, Magnetic Resonance Imaging (MRI), Computed Tomography (CT) scan, or high-frequency electrical heat (diathermy).

Section 9.13: Back-up Kits

- ~~Fiasp® FlexTouch® pen injector (supplied by Novo Nordisk)~~
- ~~Needles (to be used with Fiasp® pen injector FlexTouch®)~~
- ~~Urine sticks for ketone monitoring~~

Subjects will also be encouraged to always carry the BG - meter, *Ketone meter* and test strips.

Section 9.15: Discharge criteria

The discharge of subjects from the “in-patient” period (during which subjects will be at a designated place such as a hotel) is at the discretion of the PI. In order to make the evaluation whether it is safe for the subjects to continue to the “out-patient” period of the trial, the PI may rely on data that include but are not limited to: hypoglycaemic episodes, the number of times carbohydrates are taken by subjects to prevent or treat hypoglycaemic episodes and time in low interstitial glucose (defined as < 54 mg/dL; 3 mmol/L). *Subjects will not be discharged if they have any severe hypoglycaemic episode possibly/probably related to investigational medicinal product and/or investigational medical device in the last 24 hours.*

In the event of diabetic ketoacidosis or ≥ 2 episodes of severe hypoglycaemia, possibly/probably related to investigational medicinal product and/or investigational medical device, the subject will discontinue the trial treatment as per section 8.1.

Section 9.16: Remote Monitoring

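### Amendment 1's trial-stopping criteria (8.1.4) count only iLet-related events, so serious events or ketoacidosis rated insulin-only do not count toward the one mandatory suspension of all subjects

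*Combined protocol and SAP*

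**What the plan says.** Amendment 1 introduces a trial-level rule in 8.1.4. If any one of three criteria is met, "the PI must suspend the further treatment of all subjects via the" iLet and inform the sponsor within 24 hours. Subjects go back to their usual pump therapy while the sponsor's safety committee decides whether to stop the trial. The criteria are:

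- Serious adverse events: "≥3 subjects experience any serious adverse events possibly/probably related to investigational medical device".
- Severe hypoglycaemia: the same threshold of three subjects and the same restriction to the investigational device.
- Ketoacidosis: "≥3 subjects experience any diabetic ketoacidosis possibly/probably related to investigational medical device".

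The investigational device is the iLet (section 7.1.2).

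For individual subjects the amendment casts the net wider. Section 8.1 item 6 requires discontinuation for "Diabetic ketoacidosis possibly/probably related to investigational medicinal product and/or investigational medical device". Item 5 applies the same relatedness clause to two or more severe hypoglycaemic episodes. Section 9.15 uses it twice, once in the discharge rule ("Subjects will not be discharged if they have any severe hypoglycaemic episode possibly/probably related to investigational medicinal product and/or investigational medical device") and once when repeating the discontinuation rule.

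The stated reason for the amendment is to address FDA "comments received during the Investigational Device Exemption (IDE) review". No reason is given for using one scope at subject level and another at trial level.

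**The concern.** The two scopes were written in the same amendment for overlapping events, and the narrower one sits in the rule with the widest consequence. An event that the investigator attributes to the insulin and not to the iLet can force one subject off treatment, but adds nothing to the count that would pause everyone.

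What is at stake is the fixed pause. Fast-acting insulin aspart is itself under study here: section 3.2.2 says it is not approved for pump use in the US, and section 5.1 defines the treatment as the t_max setting combined with this insulin. A cluster of serious events put down to the insulin would be a reason to hold the other subjects until someone has looked, and the plan leaves that to discretion.

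**Working it through.** The documents give no operating characteristic for this rule, so there is no figure to reproduce. The check is a comparison of the text, followed by applying the rules to defined cases.

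**Step 1: scope of each rule.**

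| Rule | Level | Relatedness that counts | Consequence |
|---|---|---|---|
| 8.1 items 5 and 6 (Amendment 1) | Subject | Insulin and/or device | Mandatory discontinuation |
| 9.15, two sentences (Amendment 1) | Subject | Insulin and/or device | No discharge; discontinuation |
| 8.1.4, three criteria (Amendment 1) | Trial | Device only | Mandatory suspension of all subjects |
| 8.1.1 (protocol) | Cohort | Any cause; only severe hypoglycaemia and time below 54 mg/dL | Next cohort not opened |

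Four of four subject-level statements are wide, and three of three trial-level criteria are narrow. Amendments 2, 3 and 4 change sections 5.1, 1.2.3, 5.2, 6.1 and 9.11, and none touches 8.1.4.

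**Step 2: does the action require a device-only trigger?** "Dose modification is handled autonomously by the" iLet (section 7.2), and the iLet delivers the trial insulin (section 7.1.1, Table 7-1). Suspending iLet treatment therefore stops the trial insulin as well. The decision then goes to the sponsor's safety committee, and the only one that Appendix 3 describes is the committee for fast-acting insulin aspart. Neither the action nor the deciding body needs a device-only count.

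**Step 3: apply the rules to three subjects.**

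- Ketoacidosis in each, rated insulin-only. Under 8.1 item 6, 3 of 3 are discontinued. Under 8.1.4 the ketoacidosis count is 0, and the SAE count is also 0 even if all three are serious.
- A serious allergic reaction in each, rated insulin-only (section 3.3 lists systemic allergic reactions as an anticipated risk). No listed item of 8.1 applies, although section 8 lets the investigator discontinue them. The 8.1.4 count is 0.
- One severe hypoglycaemic episode in each, rated insulin-only. Item 5 of 8.1 is not met, because it needs two episodes in one subject. The 8.1.4 count is 0. If all three are in one cohort, at least two share one of its two t_max settings, so 8.1.1 blocks the next cohort, but only after every subject in the cohort has completed visit 4.
- Ketoacidosis in each, rated possibly related to both insulin and iLet. The 8.1.4 count is 3, and suspension is mandatory.

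The last case differs from the first only in the causality rating.

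**Step 4: which criterion matters most?** Amendment 1 states: "All severe hypoglycaemic episodes are qualified as SAEs and should be reported on the AE form". Criterion 1 (any SAE) therefore already contains criterion 2 (severe hypoglycaemia), so the wording of criterion 1 carries most of the effect. Ketoacidosis is not declared an SAE by rule, so criterion 3 keeps a role of its own.

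**The case against.** The strongest defence is that the rules have different purposes. The subject-level rules protect one person, so a wide trigger is natural. The trial escalates a setting of the device algorithm while the insulin is the same in every arm and cohort, and the amendment answers a device review. A rule that suspends the device on device-related events is coherent, and the regulator's comments are not in the documents. This stands as far as motive goes: the narrower scope may be intended. A reader might infer an oversight from the missing explanation, but silence does not establish one.

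Second, few events should fall in the gap. Appendix 4 rates a relationship as possible when it is conceivable and cannot be dismissed, and the iLet controls all dosing. For hypoglycaemia and hyperglycaemia, section 3.3 names sensor, t_max, pump and infusion-set causes, not insulin defects. Known or suspected hypersensitivity is an exclusion criterion. This stands too. A reader might infer that 8.1.4 would miss much of the severe hypoglycaemia or ketoacidosis in this trial. The documents point the other way, since most such events should be rated at least possibly device-related.

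Third, other safeguards exist. SAEs reach the sponsor within 24 hours (9.2.1), the insulin safety committee does ongoing surveillance, the sponsor may terminate at any time (Appendix 3), and 8.1.1 counts severe hypoglycaemia whatever its cause. A reader might therefore wrongly infer that insulin-related events go unwatched. But these provisions give awareness and discretion. The rule in 8.1.1 acts only at cohort end, pauses nobody on treatment, and does not cover ketoacidosis or allergy. None replaces a fixed pause.

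**Conclusion.** The point holds in a limited form. Serious events, including ketoacidosis, that are rated related to the insulin but not to the iLet do not count toward the only rule that requires suspension of all subjects, although the same amendment counts insulin-related severe hypoglycaemia and ketoacidosis at subject level. The difference in wording is certain. Whether it was intended cannot be settled from the documents.

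The size can be stated only as a count: any number of subjects with insulin-only events contributes 0 toward the threshold of 3. A change in the chance of suspension would need the rate of related serious events and the share rated insulin-only. The documents give neither, so no probability is offered.

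The conclusion assumes that investigators would sometimes rate an event as insulin-only, which Appendix 4 permits but which should be uncommon. This is a minor point, worth a wording change because few would object to a pause after three insulin-related serious events among 24 subjects.

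**What to change.** In each of the three 8.1.4 criteria, replace the device-only relatedness clause with the one that closes 8.1 item 6, so that events related to the insulin and/or the iLet count. Keep the threshold of three subjects, the 24-hour notice and the existing committee. If the narrower scope is intended, one sentence in 8.1.4 giving the reason would serve instead.

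The text change is four added words in each of three lines. No new data are needed, since Appendix 4 already asks for causality against the relevant trial products, using both the insulin brochure and the iLet risk document. It does need an amendment with IRB/IEC approval (Appendix 3).

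The real cost is in conduct. A pause becomes slightly more likely, including for insulin-related SAEs that are not glycaemic. Treatment periods last 7 days, the primary endpoint covers day 1 to day 7, and subjects are not replaced (8.2.1, 10.1), so a mid-period suspension could lose crossover data from a cohort of eight.

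The change would still not count events attributed only to the infusion set, the CGM or the back-up Fiasp pen, all of which are non-investigational.

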Appendix 3: Trial governance considerations

1) Regulatory and ethical considerations

- This trial will be conducted in accordance with the protocol and with the following:
 - Consensus ethical principles derived from international guidelines including the Declaration of Helsinki¹¹ and applicable ICH Good Clinical Practice (GCP) Guideline¹² and ISO 14155¹³ and 21CFR¹⁴.

Appendix 4: Adverse events: definitions and procedures for recording, evaluation, follow-up, and reporting

Important medical event:

The following adverse events must always be reported as SAEs using the important medical event criterion, if no other seriousness criteria are applicable:

- suspicion of transmission of infectious agents via the trial product.
- risk of liver injury defined as alanine aminotransferase (ALT) or aspartate aminotransferase (AST) >3 x UNL and total bilirubin >2 x UNL, where no alternative aetiology exists (Hy's law).
- *Severe hypoglycaemic episodes (see Appendix 7 for definition)*

Reporting of AEs for Non-investigational medical devices provided by Novo Nordisk for use in the trial

[figure not shown]

Reporting of AEs on Contour® Next One BG meter, Precision Xtra® ketone meter, Contact™ detach infusion set and Dexcom G5® CGM device:

All complaints (including AEs) should be reported directly to the manufacturer.

3 Changes to subject informed consent

Figure 1 - Overview of study visits and phone contacts.

Visit Schedule

Trial period	Screening	Study Treatment Period 1 (7 days)			Study Treatment Period 2 (7 days)			Not on study treatment	Follow up
Location Clinic, At home, phone   									
Day number	-35 to -14	1	2-7	8	9-14	15	16-21	22	
Visit Number	Visit 1	Visit 2		Visit 3		Visit 4		Phone Contact	
Reminders	Bring all study drugs and equipment								
	Bring diary back to clinic								
	Change infusion set and reservoir every 2 days								
	Medical history								
	Body measurements								
Assessments	Physical exam including vital signs								
	Blood sample								
	Overnight stay at a hotel								
	Change of CGM sensor								
	First day on new insulin delivery setting via iLet™								

Visit Schedule								
Trial period	Screening	Study Treatment Period 1 (7 days)		Study Treatment Period 2 (7 days)			Not on study treatment	Follow up
Location Clinic, At home, phone   								
Day number	-35 to -14	1-2	3-7	8-9	10-14	15	16-21	22
Visit Number	Visit 1	Visit 2		Visit 3		Visit 4		Phone Contact
Bring all study drugs and equipment								
Bring diary back to clinic								
Change infusion set and reservoir every 2 days								
Medical history								
Body measurements								
Physical exam including vital signs								
Blood sample								
Overnight stay at a hotel								
Change of CGM sensor								
First day on new insulin delivery setting via iLet™								

Section: Across the entire document

~~24 hours~~ 2 days including 2 overnight stays

Section: 6: What might the benefits be to you?

- Ketone meter and strips

Protocol Amendment
no 2
to Protocol, version 2
dated 07 June 2018 & Protocol Amendment 1 dated 11 July 2018

Trial ID:NN1218-4360

**An Exploratory Trial investigating the Safety and Efficacy of Fast-acting Insulin Aspart in a
Closed-loop Insulin Delivery System (bionic pancreas) in Adults with Type 1 Diabetes**

Trial phase: 2
Applicable to all countries

Table of Contents

1	Introduction including rationale for the protocol amendment.....	3
2	Changes to protocol	3

1 Introduction including rationale for the protocol amendment

This protocol amendment will serve to address the comments raised by the health authorities, specifically the US Food and Drug Administration (FDA) comments received during the Investigational Device Exemption (IDE) review.

The change is mainly related to safety of the subject.

In this protocol amendment:

- Any new text is written *in italics*.
- Any text deleted from the protocol is written using ~~strike through~~.

2 Changes to protocol

Section 5.1 Overall design

For each subject, an ‘in-patient’ period is implemented for the first 2 days (48 hours \pm 6 hours) following treatment initiation, i.e. at visit 2 and at cross-over visit (visit 3). This entails that subjects will stay at a designated place (such as a hotel) for the specified duration and will be discharged following PI’s evaluation see section 9.15. This period is included in the 7 days treatment period. The ‘out-patient’ period is defined as the period after the discharge from the designated place where the subject stays during the ‘in-patient’ period and until the end of treatment. During the ‘in-patient’ period, *subjects will be under close supervision, for at least 4 hours following their first meal, as well as during the initial period following initialization of the iLet™*. Subjects will be allowed to leave the designated place during the day but they will be restricted to the area immediately surrounding the designated place (e.g. within 15mins walk).

Protocol Amendment

no 3

**to Protocol, version 3
dated 23 Jul 2018**

Trial ID: NN1218-4360

**An Exploratory Trial investigating the Safety and Efficacy of Fast-acting Insulin Aspart in a
Closed-loop Insulin Delivery System (bionic pancreas) in Adults with Type 1 Diabetes**

**Trial phase: 2
Applicable to *all countries***

Table of Contents **"Double click to update Table of Content"**

1	Introduction including rationale for the protocol amendment.....	3
2	Changes	3

1 Introduction including rationale for the protocol amendment

For this exploratory trial with a specific purpose of establishing the safety of the iLet™ with modified settings when using faster aspart, it is deemed appropriate to limit the patient population in terms of how low the HbA_{1c} can be to enter the trial. Patients with a relatively low HbA_{1c} (lower than 6.5%) are in good control and may not be the ones who will benefit the most from the iLet™ system.

While reducing the lower level of HbA_{1c}, the upper level is being increased to allow subjects with a slightly higher HbA_{1c} (9%) to enter the trial. Those subjects are deemed to have similar safety risks/benefit compared to subjects with a lower HbA_{1c}.

To accommodate for the recruitment of the subjects with the now restricted HbA_{1c} criteria, the number of screened patients is increased from 32 to 56 subjects.

In this protocol amendment:

- Any new text is written *in italics*.
- Any text deleted from the protocol is written using ~~strike through~~.

2 Changes

Section 1.2.3 Number of subjects

Approximately ~~32~~ 56 subjects will be screened to achieve 24 randomised subjects.

Section 5.2 Subject and trial completion

Approximately ~~32~~ 56 subjects will be screened to achieve 24 subjects randomly assigned to two treatment sequences i.e. the default t_{max} setting followed by the non-default t_{max} setting or the non-default t_{max} setting followed by the default t_{max} setting all in combination with fast-acting insulin aspart.

Section 6.1 Inclusion criteria

9. HbA_{1c} is $\geq 6.5\%$ (47 mmol/mol) and ~~equal to or below~~ $\leq 8.5\%$ (~~69 mmol/mol~~) 9% (75 mmol/mol) at screening

Documentum ObjectID : 

This is a representation of an electronic record that was signed electronically and this page is the manifestation of the electronic signature.

Document signed by:

Initials	Full Name	Date and Time of Signature (Server Time)

Protocol Amendment no 4
Trial ID: NN1218-4360

~~CONFIDENTIAL~~

Date:	21 January 2019
Version:	1.0
Status:	Final
Page:	1 of 4

Novo Nordisk

Protocol Amendment

no 4

**to Protocol, version 4
dated *19 Dec 2018***

Trial ID: NN1218-4360

**An Exploratory Trial investigating the Safety and Efficacy of Fast-acting Insulin Aspart in a
Closed-loop Insulin Delivery System (bionic pancreas) in Adults with Type 1 Diabetes**

**Trial phase: 2
Applicable to *all countries***

~~This confidential document is the property of Novo Nordisk. No unpublished information contained herein may be disclosed without prior written approval from Novo Nordisk. Access to this document must be restricted to relevant parties.~~

Table of Contents **"Double click to update Table of Content"**

1	Introduction including rationale for the protocol amendment.....	3
2	Changes	3

1 Introduction including rationale for the protocol amendment

In this trial the subjects will be using a blood glucose (BG) meter that has the capacity to store the date, time and values of all BG measurements taken in course of the trial. This data can be downloaded to the site computer at the site.

Following discussions at the investigator meeting, the sponsor and the investigator are in agreement that the data downloaded from the BG meter is a more accurate representation of the glucose values measured during the trial, than a collection of the data entered by the subjects in the subject diary, as the latter is a source to potential human error.

Hence, this amendment aims to modify the way of recording BG values used for CGM calibration in the subject's diary. The subject diaries will be modified to include only the date and time of the twice daily CGM calibrations performed by the subjects. This subject-entered time will be considered the approximate time, and will be used by the site staff to identify the corresponding actual time and glucose values in the downloaded BG meter data. Only the accurate dates, times, and values for CGM calibrations from the BG meter download will be entered into the CRF by the site staff. As a consequence, the subject will not be asked to correct the diary entries in case of a discrepancy with the BG meter download.

In this protocol amendment:

- Any new text is written *in italics*.
- Any text deleted from the protocol is written using ~~strike through~~.

2 Changes

Section 9.11 Self-measured plasma glucose

Subjects will be provided with a BG meter including auxiliaries as well as instructions for use. The subjects will be instructed in how to use the device and the instruction should be repeated, if needed

The BG meters use test strips calibrated to plasma values. Therefore, all measurements performed with capillary blood are automatically calibrated to plasma equivalent glucose values, which will be shown on the display.

The BG meter provided by Novo Nordisk should be used for the measurements required in the protocol. SMPGs must be performed to calibrate the CGM sensor (section 9.10) and in the event of hypoglycaemic episode (Appendix 7) and should *for the latter* be reported in the diary, see section 9.14.

~~All SMPGs values must be recorded in the paper diary. In addition to paper diary, SMPGs performed for the calibration of the CGM sensor must also be recorded on the StudyPhone with~~

~~CGM app. The record of each SMPG value on paper diary should include date, time and value. All data from the diary must be transcribed into the CRF during or following the contact.~~

The subjects should use the SMPG values for the calibration of the CGM sensor by entering the measured values into the StudyPhone with CGM app. The record of these calibrations on paper diary should include date and time. The subjects must be instructed to bring the BG meters to the site at every site visit. The site will download the BG meter data at every site visit. Further the site will use the date and time reported by the subjects in the diary to identify the correct date, time and value in the data downloaded from the BG meter and report these in the CRF.

Documentum ObjectID : 

This is a representation of an electronic record that was signed electronically and this page is the manifestation of the electronic signature.

Document signed by:

Initials	Full Name	Date and Time of Signature (Server Time)
Meaning
